**Double-Blinded Randomized Prospective Trial of Intranasal Capsaicin Treatment for Non-
Allergic Irritant Rhinitis**

NCT02493257

Version Date: 11/18/2019

IRB NUMBER: HSC-MS-14-0173
IRB APPROVAL DATE: 11/18/2019

Protocol Title: Double-Blinded Randomized Prospective Trial of Intranasal Capsaicin Treatment for Non-Allergic Irritant Rhinitis

Principal Investigator: [name]

Co-Investigators: [name] PhD; [name]; [name]

Study Coordinator: [name] PhD

Population: The study population will consist of patients with non-allergic irritant rhinitis (NAIR) as defined by history (symptoms of nasal congestion, rhinorrhea, nasal itching or sneezing upon exposure to nasal irritants) and positive optical rhinometer (Rhinolux™, Rhios GmbH, and Germany) response with intranasal challenge with capsaicin. Participants will be sought from those presenting to the outpatient Otolaryngology clinic at the University of Texas Medical School at Houston. Patients included in the study will be between the ages of 18 and 70 with no history of sinonal surgery, intranasal steroid use for more than 4 weeks, intranasal or systemic antihistamine for 3 days, intranasal or systemic decongestants for 3 days, chronic rhinosinusitis, inflammatory or granulomatous diseases, asthma, allergic rhinitis, immunocompromised state or radiation to the head and neck.

Sample size: 11 participants will need to be recruited to each group (experimental and control) to detect a significant post-treatment change. In order to reach our target enrollment of 22 participants we expect to screen 60 subjects.

Number of sites: single site

Study duration: 13 weeks

Subject duration: 13 weeks

General Information: The proposed study seeks to investigate the effect of intranasal capsaicin treatment in patient with Non-allergic irritant rhinitis (NAIR), as well as evaluate optical rhinometry (ORM) as a means to quantify symptomatic improvement in NAIR patients during and after treatment.

Background Information:

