Multiple studies have demonstrated that intranasal capsaicin can improve nasal symptoms of NAIR patients (11-13). Regarding the usage of capsaicin, there is a product on the market: Sinus Buster which has capsaicin as the active ingredient. Numerous research papers have evaluated the efficacy and safety of Sinus Buster for the treatment of congestion in non-allergic rhinitis patients (5, 12). However, the diagnosis of NAIR in these previous studies was based primarily on history. In addition, the primary outcome in these studies was symptomatic without any objective evaluation. The goal of this study will be two-fold: with patients objectively identified as NAIR patients via the optical rhinometer, we will re-evaluate the therapeutic action of intranasal capsaicin on the management of rhinitic symptoms. We expect that the patients will show significant improvement in their symptoms. We will then use optical rhinometry as a means to objectively monitor changes in symptoms in NAIR patients. We expect that post treatment, patients will no longer have the positive response previously seen on intranasal capsaicin challenge before receiving treatment. We hope to be able to establish optical

rhinometry as an objective measurement of symptom improvement for NAIR symptoms, along with the subjective patient surveys.

Objectives:

1. To establish optical rhinometry as an objective means of evaluating changes of NAIR symptoms after treatment.
2. To re-evaluate the therapeutic action of intranasal capsaicin on the management of rhinitic symptoms in objectively defined NAIR patients.

Study Design:

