The study will consist of patients with non-allergic irritant rhinitis (NAIR) as defined by history (symptoms of nasal congestion, rhinorrhea, nasal itching or sneezing upon exposure to nasal irritants) and positive optical rhinometer (Rhinolux™, Rhios GmbH, and Germany) response with intranasal challenge with capsaicin (17). Participants will be sought from volunteers and those presenting to the outpatient Otolaryngology clinic at the University of Texas Medical School at Houston. Patients included in the study will be between the ages of 18 and 70 with no history of sinonasal surgery, intranasal steroid use for more than 4 weeks, intranasal or systemic antihistamine for 3 days, intranasal or systemic decongestants for 3 days, chronic rhinosinusitis, inflammatory or granulomatous diseases, asthma, allergic rhinitis, immunocompromised state or radiation to the head and neck.

Allergy Testing to Identify and Exclude Subjects with Allergic Rhinitis

All previously consented subjects with history consistent with NAIR will be screened with a skin prick test (Multi-Test II Lincoln Diagnostics, Decatur, IL USA) to 6 common allergens including dust mite, mixed mold extract, cat hair, grass pollen, insect extracts, and bermuda grass extract to exclude allergic rhinitis. Those with confirmed negative skin prick testing will be eligible for the study.

Capsaicin Challenge and Optical Rhinometry

The optical rhinometer apparatus is applied to either side of the nasal dorsum according to the manufacturer's instructions. A one-minute baseline recording will be obtained and averaged. Capsaicin solution (Sigma Chemical, St. Louis, MO USA) will be diluted in 1% ethanol vv and 0.9% normal saline. 1% ethanol in 0.9% normal saline will serve as the vehicle solution. A mucosal atomizer device (MAdomizer, Wolfe Tory Medical, Inc Salt Lake City, UT USA delivering a 100 μ l solution will be used to deliver a dose of capsaicin totaling 1.5 μ g of capsaicin (0.05 mM) to the anterior face of the inferior turbinate of each nare. The maximum change in optical density (OD) will be recorded. Patients with a maximum change in OD of at least 0.2 will be considered a positive response and included in the study.

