A composite symptom score will be recorded based a commonly used rhinitis rating system as recommended by the FDA for clinical trial studies on allergic rhinitis (<http://www.fda.gov/downloads/Drugs/GuidanceComplianceRegulatoryInformation/Guidances/ucm071293.pdf>). Each of the following 4 symptoms: nasal itching/tingling, nasal congestion, sneezing and rhinorrhea, will be rated on a 0-3 scale of severity (Appendix B) and a summed composite score will be recorded for each subject.

Capsaicin Treatment Concentration

The capsaicin solution will be prepared by using the formula previously reported by Van Rijswijk et al; (0.1mmol/l) diluted in ethanol and 0.9% normal saline (19). Using the MAD, 0.8mL will be delivered to each nasal cavity for a total of 24.4 ug per nasal cavity.

Study Procedure:

[figure not shown]
There will be a total of 4 visits. On the first visit, patients will be consented and undergo skin prick testing, the capsaicin challenge and Optical Rhinometry. Prior to undergoing the capsaicin challenge, a composite symptom score will be recorded. Patients with confirmed negative skin prick testing, and positive response on ORM will be eligible for the study and will be asked to return for treatment. Those who are not eligible will not be responsible for any costs associated with screening and will be compensated for parking as well as \$25.00 for their time.

At the second visit, the NAIR patients will have been randomized and blinded into two groups: Group A will be treated with vehicle spray; and Group B will be treated with the capsaicin spray. The PI will be blinded to the treatment. A member of the research team, which consists of Drs. [name], [name], [name], and [name] (research coordinator), will assist during the randomization and distribution of appropriate pre-made medications so that the PI and subjects remain blinded.

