5 consecutive applications of capsaicin or placebo will be administered intranasally, with 1 hour between each application. Fifteen minutes prior to each application of medication, the nasal mucosa will be anesthetized with 100 ul of 1% lidocaine will be applied to each nasal cavity via MAD for all study participants. The lidocaine should not alter the nasal mucosa reaction to capsaicin; and is meant to anesthetize the area from the mild stinging of capsaicin. In fact, because lidocaine has a very mild stinging sensation at times; it can serve to mask the stinging one may get with intranasal capsaicin. Using the MAD, 100 μ L of 1% ethanol in 0.9% saline solution (Group A) or 0.8 mL solution with (0.1mmol/l) of capsaicin in 1% ethanol in 0.9% saline (Group B) will be delivered to each nasal cavity. On this day, they will not need to undergo optical rhinometry. Patients will fill out composite symptoms scores before and five minutes after 1st and 5th treatments. Patients who complete this portion of the experiment will receive \$50 dollars in compensation as well as parking.

Patients will then follow up 4 and 12 weeks after initiating treatment. At the 4 week and 12 week follow-up appointments, subjects will undergo capsaicin challenge followed by ORM and composite symptom score of nasal symptoms will be reported. Patients who complete both follow up visits will receive \$25 dollars in compensation as well as parking.

Study Protocol

Compensation:

In summary, patients that undergo the screening process and complete the skin prick testing and intranasal capsaicin challenge and ORM will be compensated \$25 as well as parking validation. Patients that undergo the treatment will be compensated \$50 plus parking for completing that day. Patients that complete the study and return 4 and 12 weeks post treatment, will be compensated \$25 plus parking.

Data and Safety Monitoring:

Previous studies have shown that the concentration of capsaicin that will be used is generally well tolerated.

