Regarding the lidocaine, it is administered routinely in our clinic prior to nasal endoscopy and flexible laryngoscopy exams. Side effects can include minor stinging and burning when applied to the nose. Because it is an intranasal spray, there is a risk that patients will swallow it and may have difficulty swallowing for up to 45 minutes after application. We express to patients that they should avoid eating or drinking anything up to 45 minutes after the lidocaine application.

Regarding skin prick testing, patients may have mild discomfort where the skin is pricked. They may have symptoms such as itching, a stuffy nose, red watery eyes, or a skin rash. Rarely, people can have anaphylaxis, but this usually only occurs with intradermal testing, which we will not be performing. If patients become short of breath, we do have oxygen available in the clinic.

Patients will be educated to call the outpatient Otolaryngology clinic at the University of Texas Medical School at Houston if there are any adverse effects.

Human Subjects:

Participants will be sought from those presenting to the outpatient Otolaryngology clinic at the University of Texas Medical School at Houston. Patients included in the study will be between the ages of 18 and 70 with no history of sinonasal surgery, intranasal steroid use for more than 4 weeks, intranasal or systemic antihistamine for 3 days, intranasal or systemic decongestants for 3 days, chronic rhinosinusitis, inflammatory or granulomatous diseases, asthma, allergic rhinitis, immunocompromised state or radiation to the head and neck.

This is a small study of only 22 subjects total and as addressed previously we anticipate screening 60 subjects in order to complete our enrollment. . Our practice consists of adult patients with a majority of who speak and read English. Therefore, it is unlikely to exclude a subject from the study because they do not speak or read English

Statistical Analysis:

Justification of sample size:

Using [name] paper (17) : his article showed the average maximum optical density in NAIR patients was 0.2 (SD 0.051), seen when using the 0.05 mM concentration of capsaicin during the capsaicin challenge and ORM. Healthy control subjects had a mean maximal OD change of 0.174 (SD 0.034). This was significant to $p=0.01$. Based on this data, 11 patients will need to be recruited to detect a significant post-treatment change.

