Student's t-test will be used to compare the mean change in composite symptom scores pre and post-treatment in both groups. Student's t-test will also be used to compare changes in maximal optical density in response to capsaicin challenge pre- and post-treatment in both

groups. Statistical significance will result if $p < 0.05$. The Spearman Rank Correlation will be used to analyze associations between composite symptom scores and changes in OD.

Ethics:

IRB approval will be sought from CPHS

Data Handling and Record Keeping: In order to maintain confidentiality, a data sheet with patient's names and data collected for the study (see data sheet) will be stored in a locked file cabinet within the department of Otorhinolaryngology. Access to data sheets in patient will be limited to co-investigators and research coordinator. Only de-identified data or collective data will be shared.

Quality control and assurance: In order to confirm that the diagnosis of non-allergic irritant rhinitis is accurate and made in an unbiased manner, a history of rhinitic symptoms will be confirmed with objective skin testing.

All datasheets will be recorded by PI and reviewed by at least one of the other 3 co-investigators to ensure accuracy in the recording of clinical data.

Publication Plan: This study has been funded by the American Association of Otolaryngic Allergy (AAOA) Foundation Grant. Results from this study will be presented at a future AAOA national meeting and initial publication rights will be given to the International Forum of Allergy and Rhinology.

All enrolled subjects will be notified of any publication resulting from this study, but these publications will present data on only the aggregate group.

REFERENCES

2. Hummel T. Assessment of intranasal trigeminal function. *Int J Psychophysiol*. 2000 May;36(2):147-55.

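### The Statistical Analysis section does not say whether efficacy is tested between capsaicin and vehicle or pre/post within each arm, and the within-arm optical density test would be biased towards a fall

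*Combined protocol and SAP*

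**What the plan says.** Under Study Procedure, "Group A will be treated with vehicle spray; and Group B will be treated with the capsaicin spray". The second objective is "To re-evaluate the therapeutic action of intranasal capsaicin on the management of rhinitic symptoms in objectively defined NAIR patients".

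The Statistical Analysis section gives two t-test sentences. One uses Student's t-test to "compare the mean change in composite symptom scores pre and post-treatment in both groups". The other says a "t-test will also be used to compare changes in maximal optical density in response to capsaicin challenge pre- and post-treatment in both" groups. Significance is p < 0.05. Neither sentence says paired or two-sample, one- or two-sided, or week 4 or week 12, although both follow-up visits include a challenge with rhinometry and a symptom score.

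The Sample size entry at the front says "11 participants will need to be recruited to each group (experimental and control) to detect a significant post-treatment change". The Justification of sample size says "11 patients will need to be recruited to detect a significant post-treatment change". Background Information states the expected result as patients losing the positive response they had before treatment, and does not mention vehicle there.

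On the OD baseline, Capsaicin Challenge and Optical Rhinometry says "Patients with a maximum change in OD of at least 0.2 will be considered a positive response and included in the study". Of the treatment visit, Study Procedure says "On this day, they will not need to undergo optical rhinometry".

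**The concern.** A randomised, vehicle-controlled trial should name the comparison that answers its efficacy objective, and this one does not. Two analysts could each follow the text and reach different conclusions from the same data: one compares change between arms, the other tests change from baseline separately in each arm.

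The second route loses what randomisation provides. A fall in symptoms or OD on capsaicin alone may be placebo response, vehicle effect or natural course. OD has a further problem: patients are admitted because one reading was high, and that same reading then serves as baseline. Some of the later fall is then expected without any treatment. It could be reported as efficacy, or as evidence that rhinometry tracks improvement.

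**Working it through.** **1. Does the text settle the reading?**
- For between-arm: what is compared is a change, which is already post minus pre; the word paired never appears; there is a randomised vehicle arm; and the Sample size entry counts each group, experimental and control.
- For within-arm: pre- and post-treatment are the terms named; both sample-size statements aim at a post-treatment change; and the expectation in Background Information is before/after.
- Neither set excludes the other.

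**2. Does the sample size settle it?** Its inputs are NAIR mean 0.2 (SD 0.051) and control mean 0.174 (SD 0.034), a gap of 0.026. No power is stated.
- Two-sample, two-sided 5%, 80% power: n = 2 × (1.96 + 0.842)² × (SD/0.026)² gives 61 per arm for SD 0.051, 44 for the pooled SD 0.0433, and 27 for SD 0.034.
- One-sample, with SD of change set equal to those SDs: 31, 22 and 14.
- Eleven appears only with choices the plan does not state. One example is one-sample, one-sided, SD 0.034: (1.645 + 0.842)² × (0.034/0.026)² = 10.6, rounded up to 11.

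So the figure of 11 does not show which contrast was meant.

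**3. Direction of the within-arm OD bias.** Let x be screening OD with population mean μ and SD σ, and let a retest without treatment have the same mean and SD and correlation r with x. Then E(retest | x) = μ + r(x − μ), and the expected fall among those enrolled is (1 − r) × [E(x | x ≥ 0.2) − μ]. This is positive for any r below 1.

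**4. Size, for illustration.** Assumptions not in the documents: normal OD, the values of r, and the screened mean.

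With μ = 0.2 and σ = 0.051 the cut-off sits at the mean. The enrolled mean is 0.2 + 0.051 × √(2/π) = 0.2407, so the expected fall is (1 − r) × 0.0407. The variance of change is (1 − r)² × 0.051² × (1 − 2/π) + (1 − r²) × 0.051². At r = 0.5 the fall is 0.0203 and the SD of change 0.0468. With 11 patients the standard error is 0.0468/√11 = 0.0141, so the null fall is about 1.4 standard errors.

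Simulated trials with no treatment effect, 11 per arm, one visit, two-sided 5%:

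| r | 0.3 | 0.5 | 0.7 | 0.8 | 0.9 |
|---|---|---|---|---|---|
| Expected fall, mean 0.2 | 0.028 | 0.020 | 0.012 | 0.008 | 0.004 |
| SD of change, mean 0.2 | 0.053 | 0.047 | 0.038 | 0.031 | 0.022 |
| Within-arm rejection, mean 0.2 | 36% | 26% | 16% | 12% | 8% |
| Within-arm rejection, mean 0.251 (1 SD above cut-off) | 8% | 7% | 6% | 6% | 5% |
| Between-arm rejection, either mean | 5% | 5% | 5% | 5% | 5% |

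With the mean at 0.2 nearly all within-arm rejections are falls, for which the nominal rate is 2.5%.

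**5. Power of the between-arm test.** Under the same model with mean 0.2, 11 per arm and a true difference of 0.026 (the only gap the sample-size paragraph gives), power is about 19%, 24%, 34%, 46% and 73% for r = 0.3 to 0.9.

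**The case against.** The strongest reply is that the harmful reading is not the natural one. Comparing changes across two groups ordinarily means a two-sample test, the trial is blinded against vehicle, and on that reading the error rate is about 5%. This stands. A reader might infer that the plan prescribes within-arm tests or discards its control arm; the documents do not support that. They leave the contrast open.

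Second, the OD bias does not bear on the symptom objective. This also stands. Entry has no symptom-score threshold, so the selection argument does not carry over. For symptoms the only point is that a within-arm change cannot separate capsaicin from vehicle.

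Third, the size rests on assumed inputs. It does. Treating 0.2 (SD 0.051) as the screened population is a choice, because the protocol does not say how the cited NAIR group was selected. No single figure in the table should be read as this trial's error rate.

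Fourth, a reader might judge between-arm power from the raw fall of 0.041 (0.241 at entry down to 0.200). That is a pre/post figure. In the same model the vehicle arm also falls, so capsaicin patients reaching 0.200 would differ from vehicle by r × 0.0407, that is 0.012 to 0.037 for r = 0.3 to 0.9, with power of about 8% to 95%.

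**Conclusion.** The concern holds as an unstated efficacy contrast. One permitted reading is valid; the other can produce a misleading result on both outcomes and a biased test on OD. The direction of the OD bias is firm provided repeat challenges follow the same distribution and retest correlation is below 1. Its size ranges from negligible to several times the nominal rate, depending on retest correlation and on where the screened population lies relative to 0.2, neither of which the documents give. The between-arm comparison is protected under every assumption tried, because both arms are selected in the same way.

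A reader might go further and conclude that 11 per arm is shown to be too few. The documents do not establish that, because they state no treatment effect between arms. What can be said is that 11 per arm is not supported for a between-arm difference of 0.026 under the correlations tried.

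**What to change.** Replace the two t-test sentences in Statistical Analysis with:

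> Change from screening in maximal OD, and change from baseline in composite symptom score, will be compared between capsaicin and vehicle by two-sample t-test (two-sided 0.05); within-arm changes are descriptive.

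Name the visit tested, week 4 or week 12, before unblinding. Revise the Justification of sample size to state the between-arm difference and the SD of change it assumes, without claiming that 11 per arm suffices for 0.026.

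No new data or visits are needed to name the contrast, and if a between-arm test was always intended the test itself does not change. The cost is not purely editorial, though: the visit has to be chosen, and an honest restatement of the sample size may show limited power at 11 per arm. Which pre-treatment symptom score serves as baseline (screening or treatment day, since both are recorded) is a separate, minor clarification that can be made in the same edit.

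### A single p<0.05 rule covers two outcomes and two follow-up visits, with no deciding outcome, visit, contrast or pre/post pair, so the chance of some false positive exceeds 5%

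*Combined protocol and SAP*

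**What the plan says.** The Statistical Analysis section names two outcomes, each with the same test. For symptoms: "Student's t-test will be used to compare the mean change in composite symptom scores pre and post-treatment in both groups". For the challenge response: "Student's t-test will also be used to compare changes in maximal optical density in response to capsaicin challenge pre- and post-treatment in both" groups. One threshold follows for everything: "Statistical significance will result if" p is below 0.05. A Spearman correlation between symptom scores and OD changes is added. The section gives no order of testing and no adjustment.

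Study Procedure sets two follow-up visits: "Patients will then follow up 4 and 12 weeks after initiating treatment". It describes their content as follows: "At the 4 week and 12 week follow-up appointments, subjects will undergo capsaicin challenge followed by ORM and composite symptom score". It also collects symptom scores on the treatment day: "Patients will fill out composite symptoms scores before and five minutes after 1st and 5th treatments". A further score is taken at visit 1, before the screening challenge.

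The Objectives list two aims, establishing optical rhinometry as a measure of change and re-evaluating capsaicin treatment, without ranking them. The sample size justification rests on OD but does not call OD primary. Where the background text speaks of a primary outcome, it means that of earlier studies.

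**The concern.** A threshold of 0.05 limits the false-positive chance to 5% for one test chosen in advance. This plan leaves four choices open: the outcome (symptom score or OD), the visit (week 4 or week 12), the contrast (change compared between arms, or pre against post within each arm, since 'in both groups' fits either), and the scores that serve as 'pre' and 'post'. An analyst could follow the section faithfully and still settle these after seeing the data.

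In a trial of 22 patients, one nominally significant result could then be presented as showing that the treatment works, with no way for a reader to tell how many other tests could have filled that place. A within-arm result is especially weak evidence of a treatment effect. Patients enter only if their visit 1 OD change is at least 0.2, so repeat values can be expected to fall somewhat without treatment.

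**Working it through.** **Inputs from the documents.** Per-test threshold 0.05; two outcomes with t-tests (Statistical Analysis); two follow-up visits (Study Procedure); two arms of 11 (Sample size).

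**Assumptions.** Two-sided tests, because sidedness is not stated. Test counts are inferred from the design. The documents give no correlations, so change scores were given correlations of 0 to 0.9 between visits and 0 to 0.7 between outcomes. No true effect exists; for within-arm tests this means no true pre/post change.

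**Starting point.** The plan gives no overall error rate. Its rule applied to one pre-named test gives 1 − 0.95 = 5%.

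**Number of tests**

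- Between arms, one visit: 2 outcomes = 2 tests.
- Between arms, both visits: 2 outcomes × 2 visits = 4 tests.
- Within arms, both visits: 2 outcomes × 2 visits × 2 arms = 8 tests.

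**If the tests were independent**, the chance of at least one p<0.05 is 1 − 0.95^k:

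- k = 2: 1 − 0.9025 = 9.8%
- k = 4: 1 − 0.8145 = 18.5%
- k = 8: 1 − 0.6634 = 33.7%

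**With correlated change scores** (100,000 simulated trials per setting, 11 per arm):

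| Correlation between visits | Correlation between outcomes | 4 between-arm tests | 8 within-arm tests |
|---|---|---|---|
| 0 | 0 | 18.6% | 33.9% |
| 0.5 | 0.5 | 16.3% | 30.4% |
| 0.7 | 0.5 | 15.3% | 28.6% |
| 0.7 | 0.7 | 13.9% | 26.5% |
| 0.9 | 0.7 | 11.8% | 22.9% |

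With one visit only, the two between-arm tests give 9.8% at outcome correlation 0 and 8.5% at 0.7.

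The ranges are therefore about 8-10% (2 tests), 12-19% (4 tests) and 23-34% (8 within-arm tests). The Spearman test and the choice among symptom scores are not counted.

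**Candidate symptom scores.** One at visit 1 (before the challenge), four on the treatment day and one at each follow-up visit make 1 + 4 + 2 = 7. No pair is designated. The visit 1 score precedes the challenge, whereas the follow-up score is listed after the challenge and rhinometry with no stated time. A change between them could mix a resting score with a provoked one.

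**After the fix.** One named between-arm test returns 5%. If the alpha is split between two outcomes at one visit, each is tested at 0.025, and 1 − 0.975² = 4.9% under independence.

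**The case against.** The section sets a per-test threshold and nowhere promises a 5% rate across tests. With two stated objectives, testing two outcomes is natural, and the gap can be described simply as a missing primary outcome and hierarchy. That is fair, and it rules out saying that the plan misstates an error rate. It does not remove the consequence: as written, the rule lets any of several tests count as success.

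The percentages are also conditional. The documents never state four or eight tests. Zero correlation between visits is implausible if both changes share the visit 1 baseline: with equal variances and equal correlations, the two changes correlate 0.5. This stands, and is why the ranges extend to strong correlation and to a single visit. No multi-test setting examined comes down to 5%.

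The within-arm figure assumes no true pre/post change in either arm. Regression to the mean in OD is a fault of that comparison, separate from multiplicity. This stands too, so the within-arm range should not be merged with the between-arm one.

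A reader might infer that the treatment-day scores are the literal 'pre' and 'post' pair. Adding two such post-scores would give 1 − 0.95^6 = 26% between arms or 1 − 0.95^12 = 46% within arms. The documents do not support this reading. The same pre/post wording is applied to OD, which is not measured on the treatment day, and the background and compensation text use 'post treatment' for later assessments. Those figures also assume independence among same-day scores from the same patients.

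A reader might also infer that OD must be the deciding outcome. It is the sample-size basis, but nothing makes it decisive. If the sample-size difference (0.2 − 0.174 = 0.026) and SDs (0.034 to 0.051) applied to the between-arm contrast, two-sided power with 11 per arm would be about 40% to 21%. An OD-first gate would then often block the symptom test.

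**Conclusion.** The concern holds. One unadjusted threshold covers two outcomes at up to two visits, and the deciding outcome, visit, contrast and pre/post pair are all unspecified. The resulting excess over 5% is modest if one visit is tested between arms (about 8-10%), larger if both are (about 12-19%), and largest if separate within-arm tests are meant (about 23-34%). These are illustrations under assumed test counts and correlations and no true effect; they are not error rates that the documents state. The structural gap does not depend on them. It should be corrected, because the choice of result would otherwise be open after the data are seen.

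**What to change.** Before unblinding, replace the significance sentence in Statistical Analysis with wording that does the following:

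1. Names one deciding test at two-sided 5%: Group B versus Group A for change from visit 1 in one outcome at one follow-up visit. Change in maximal OD is a natural candidate because the sample size is based on it, but the sponsor should choose the outcome and the visit, weighing the power figures above.
2. Tests the other outcome, same contrast and same visit, only if the first is significant. Splitting the alpha between the two outcomes is an acceptable alternative.
3. Reports the other follow-up visit, treatment-day scores and within-arm changes with confidence intervals and no significance claims.
4. Keeps the Spearman correlation, with a confidence interval, as the estimate for the objective of establishing optical rhinometry.
5. States which symptom scores are 'pre' and 'post', and reconciles the visit 1 and follow-up descriptions in Study Procedure on whether the score comes before or after the challenge.

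Items 1 to 4 change analysis wording only and need no new data. Item 5 may need a change of procedure if scores have been taken at different points relative to the challenge. The downside is that fewer results can be called significant, and the second outcome may not be formally tested.
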